9.4 International Prostate Symptom Score (IPSS)

This is an 8-item scale, widely used in clinical practice, which measures lower urinary tract symptoms. It includes questions encompassing incomplete bladder emptying, frequent urination, urgency, nocturia, intermittency, weak stream, straining, and quality of life related to urinary symptoms (73).

There are robust data to suggest that prostate cancer patients on active surveillance experience significantly decreased urinary health relative to men without prostate cancer. In a cohort analysis of 6,000 community dwelling older men, we observed that compared to men without prostate cancer, men with prostate cancer on active surveillance (i.e. those who had not undergone treatment) reported a significantly diminished quality of life due to urinary symptoms (74). In addition, several published studies have noted that high vegetable diets and higher serum carotenoid concentration are associated with decreased urinary symptoms (75-77).

9.5 Expanded Prostate Cancer Composite Index 26 (EPIC-26)

This instrument is an abbreviated version of the Expanded Prostate Cancer Composite Index (EPIC). It contains 26 questions focusing on 5 distinct health-related quality of life domains relevant to prostate cancer: urinary incontinence, urinary irritation/obstruction, bowel, sexual and vitality/hormonal. Each domain has function and other subdomains. All of the domains for EPIC-26 are reported using a 0-100 score, with higher scores representing favorable health related quality of life. The EPIC-26 demonstrates robust consistency and validity for measuring these important outcomes related to prostate cancer survivorship (78).

9.6 Nutrition Self-Efficacy Scale

The Nutrition Self-Efficacy scale assesses the degree to which individuals are confident that they can control their nutrition (79). The scale assesses perceived self-efficacy, the confidence in one's ability to meet one's goals, and coping self-efficacy, defined as optimistic beliefs about one's capability to deal with barriers that arise in plans. The scale consists of 5 items rated on a 5 point Likert scale, ranging from 'very confident' to 'not confident at all'. Internal consistency was excellent (alpha coefficient = .87, n= 1,722). Evidence of validity was provided by the Nutritional Efficacy Scale correlating significantly with nutritional behavior ($r = .34$, $p < .01$) (80). Because quality of life or anxiety has not been formally evaluated in an AS population or in the setting of a randomized clinical trial among AS patients, a battery of scores will be assessed as exploratory variables, with scores at each time point and changes in scores over time assessed between the intervention and control groups using student's t-test and linear regression modeling.

9.7 Satisfaction with the MEAL Program

At 12 and 24 months, those in the MEAL arm of the study will be asked to complete a series of questions about their satisfaction with the MEAL program (C-2008, CALGB 70807 MEAL Study Counseling Evaluation Form). All but one question has been used in WHEL, (Women's Healthy Eating and Living, the prior diet study on which this study is based). The MEAL Satisfaction Questionnaire, developed by Pierce and colleagues, includes 26 items with all items rated on Likert scales, with response categories varying by the type of question. The following areas of satisfaction are assessed: satisfaction with the nutritional plan, counseling calls, the counselor, the time and frequency of the calls, expectations that the diet will help to prevent recurrence and improve their overall health, barriers in attaining the dietary goals, and the difficulty encountered in changing and maintaining their diet. Internal consistency meets acceptable standards for the satisfaction with their food intake for the different types of food (5 questions, alpha coefficient = .71), satisfaction with the counselor (9 items, alpha coefficient = .87), and near an acceptable standard for the 2 items assessing how enjoyable and important the counseling calls have been (alpha coefficient = .69).

10.0 CORRELATIVE STUDIES

10.1 Plasma carotenoid and cholesterol analysis

10.1.1 Background

Carotenoids are organic, plant-based pigments. One of the most common carotenoids is lycopene. Lycopene is an antioxidant and free radical scavenger commonly found in tomatoes. Increased lycopene and tomato intake have been associated with decreased prostate cancer risk. An analysis of the Health Professionals Cohort observed a 21% lower prostate cancer incidence among those with the highest compared to the lowest lycopene intakes. Moreover, those with the highest frequencies of tomato and tomato-based product intake had up to a 35% risk reduction compared to those with the lowest intake (20). In a meta-analysis of 21 published studies, Etminan and colleagues observed that participants with the highest intake (fifth quintile of intake) of raw tomatoes [Relative Risk (RR) 0.89, 95% CI 0.8 to 1.0] or cooked tomatoes (RR 0.81, 95% CI 0.71 to 0.92) had a modest reduction in prostate cancer risk (10). These investigators also noted that while lycopene consumption was not associated with prostate cancer risk (RR 0.99, 95% CI 0.93-1.06), higher serum lycopene concentrations were associated with decreased risk (RR 0.85, 95% CI 0.75-0.97) (81).

Interest in the potential therapeutic benefits of lycopene and/or tomatoes has led to a small number of clinical trials that have produced promising, yet preliminary, results. Stacewicz-Sapuntzakis and Bowen placed 32 patients with prostate cancer on tomato paste-rich diet, 3 weeks before their scheduled prostatectomy. The patients consumed 26.8 mg of lycopene per day, compared with their usual mean intake of 5 mg/day. These investigators noted significant reductions in serum PSA concentrations and increases in apoptotic index in the intervention group compared with the controls (82). Similarly, Kucuk and colleagues randomized 26 patients with newly diagnosed prostate cancer to receive tomato oleoresin extract containing 30 mg of lycopene or no supplementation for 3 weeks before radical prostatectomy. When compared with the intervention group was found to have smaller tumors, less involvement of surgical margins, and less diffuse involvement of the prostate by high-grade prostatic intraepithelial neoplasia (83). Chen and colleagues observed in a radical prostatectomy model that men who consumed large amounts of tomato products prior to surgery had less oxidative damage in the prostate (30), while Barber and colleagues noted decreased PSA velocities in men with prostate cancer treated with lycopene supplementation (25).

While these data are compelling, associations of carotenoids with prostate cancer remain unclear. In the MEAL pilot study, there was no significant association of plasma lycopene or other carotenoids with plasma PSA over a 6-month period for AS patients or patients with PSA-only recurrence following surgery or radiation (40-42).

10.1.2 Objectives

- 10.1.2.1** To compare plasma carotenoid concentrations in AS patients receiving dietary intervention compared to no intervention.
- 10.1.2.2** To correlate plasma carotenoid concentrations with PSADT in AS patients.
- 10.1.2.3** To correlate plasma carotenoid concentrations with time to pathological progression in AS patients.

10.1.3 Methods

Carotenoids: The blood nutrient analysis will take place at UCSD under the direction of [REDACTED]. The carotenoid analysis will be done at UCSD. Plasma carotenoids will be separated and quantified using the HPLC methodology that we have used previously (40, 67, 68), with modifications to reduce oxidative loss and improve recovery of compounds during analysis. Standard reference materials from the manufacturer will be used to validate analytical precision of these procedures. At UCSD, samples will be stored at all times at -70° C or lower temperatures in freezers equipped with temperature alarms in the Moores UCSD Cancer Center that are under the direct supervision of [REDACTED].

Cholesterol is analyzed using the KODAK EKTACHEM DT SLIDE. The slide is a multilayered film in a plastic support. It contains all the reagents necessary to determine cholesterol level in serum or plasma. A 10 uL drop of specimen is deposited on the slide. The sample spreads evenly and diffuses into the reagent layers. Cholesterol in the sample undergoes a series of reactions in the slide to produce a colored compound. The intensity of the color is proportional to the amount of cholesterol in the sample and is measured by the KODAK EKTACHEM DT60 analyzer.

Principles of the procedure: The spreading layer distributes the sample evenly on the slide and causes the cholesterol to dissociate from lipoprotein carriers. Cholesterol esters are hydrolyzed to free cholesterol which then undergoes a series of reactions beginning with oxidation by the specific enzyme, cholesterol oxidase. In the final reaction, a colored dye is produced. By measuring the amount of light reflected from the dyed layer after a fixed incubation period, the DT60 Analyzer can calculate the amount of cholesterol present in the sample.

10.2 Serum carotenoid analyses (Substudy 151105)

Carotenoid analysis can be evaluated on plasma or serum. Therefore, in addition to the plasma sample, we will be collecting and banking serum for evaluation of carotenoids, if needed, as well as for the evaluation of other circulating markers of interest.

10.3 Polymorphism Analysis (Substudy 151105)

10.3.1 Background

Multiple genetic variants have been identified which are linked to increase risk of developing prostate carcinoma (84-89). There is increasing evidence that genetic factors could not only predispose men to prostate cancer in general but specifically for aggressive disease. For example CASP8 and MDM2 contain variants associated with risk of aggressive prostate carcinoma (90, 91). Cheng et al (92) and Beebe-Dimmer et al (93) demonstrated that at least some 8q24 variants are associated with risk of advanced disease. Duggan et al identified rs1571801, located in the DAB2IP gene, as a candidate which was associated with aggressive PCa in both European-Americans (p=0.004) and African-Americans (p=0.02) (94). Mononen et al found that 5' untranslated variant in CYP17A1 was associated with an increased risk of high grade PCa (95).

Identification of a population of patients at risk for aggressive disease is only useful if the disease can be prevented or treated effectively. Dietary manipulation holds promise as a way of preventing or ameliorating the risk of developing prostate carcinoma. There is a growing body of evidence that dietary factors may modify genetic risk. Several genes, such as *MnSOD*, *XRCC1*, and *GST*, may modify the association of specific nutrients and foods with prostate cancer risk and groups have called for further research to confirm these initial observations (96). For example, evidence from the Physicians Health Study suggests that manganese superoxide dismutase (*MnSOD*) polymorphism V16A may interact with selenium levels to modify risk of clinically aggressive PCa (97). *MnSOD* genotype were not associated with increased risk of disease. However, when they stratified the cases by prediagnostic

selenium levels they found that the cohort with the highest selenium levels and AA genotype were protected against prostate cancer in general and clinically aggressive prostate cancer specifically. Another example of genotype environment interaction is vitamin D and Vitamin D Receptor polymorphisms. A study from the Physicians Health Study demonstrated that while the Vitamin D Receptor polymorphism *BsmI* or *FokI* were not associated with prostate carcinoma, men with *FokI ff* genotype and low vitamin D levels had the highest risk of developing PCa in general and aggressive disease specifically (98). Given that vitamin D oral formulations have been explored as a treatment option for PCa (99), identification of an interaction between genotype and environment could have potential clinical application.

The MEAL study offers the ideal population to study the interaction between genetic risk and diet. First and foremost, if genetic risk is associated with aggressive disease, then patients with the high risk genetic background should be more likely to progress. What is unique about the MEAL study is to determine if dietary modification alters that genetic risk. If it does then genetically high risk patients could modify their diet at the time of diagnosis or possibly sooner. Alternatively, if diet does not modify risk of progression then more aggressive management could be instituted.

10.3.2 Objectives

10.3.2.1 To compare MnSOD, XRCC1, and GST gene polymorphisms to PSADT in AS patients receiving dietary intervention versus no intervention.

10.3.2.2 To compare MnSOD, XRCC1, and GST gene polymorphisms to time to pathological progression in AS patients receiving dietary intervention versus no intervention.

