1.9 Inclusion of Women and Minorities

Because prostate cancer occurs primarily in men above the age of 50, recruitment of participants for this study will focus upon men aged 50 years and older. Since women and children are not subject to prostate cancer, they will be excluded from this study. Efforts will be made to enroll individuals of all races and ethnic backgrounds, with the added goal of recruiting relatively high numbers of individuals of Hispanic origin and of African-American origin. The increased risk of prostate cancer and especially of lethal prostate cancer among African Americans makes it imperative that we secure adequate representation of African Americans in this study.

CALGB has a long history of effort to ensure adequate representation of minorities in all clinical trials, including prevention trials. The recent experience of the Selenium and Vitamin E Cancer Prevention Trial (SELECT) (80) is instructive: 29% of the CALGB participants were African Americans. In our MEAL pilot study, 12% of participants were non-white. Our goal with the full MEAL trial is for 29% of participants to be members of racial minorities, especially African Americans.

Racial Categories	DOMESTIC PLANNED ENROLLMENT REPORT				
	Ethnic Categories				
	Not Hispanic or Latino		Hispanic or Latino		Total
	Female	Male	Female	Male	
American Indian/Alaska Native	0	3	0	0	3
Asian	0	9	0	0	9
Native Hawaiian or Other Pacific Islander	0	1	0	0	1
Black or African American	0	53	0	1	54
White	0	381	0	16	397
More Than One Race	0	0	0	00	0

Total	0	447	0	17	464
-------	---	-----	---	----	-----

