11.0 STATISTICAL CONSIDERATIONS

11.1 Randomization

Patients will be randomized with equal probability to receive the dietary intervention (experimental arm) or dietary information (control arm). A total of 464 patients will be enrolled to this trial, 232 patients per arm. The study will take a total of 5 years: about 3 years of accrual with an expected accrual rate of 15 patients per month, and 2 years of follow-up for each patient.

Stratification factors: Randomization will be stratified by age (≤ 70 years vs. > 70 years), race (African American vs. Other) and baseline prostate biopsy (0-12 months prior to registration vs. >12 -24 months prior to registration).

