Time to Treatment: Probability to proceed to treatment within 2 years (binary observation) and time to treatment (censored time to an event observation) will be analyzed using the chi-squared test and the log-rank test, respectively. We expect that the control arm will have more patients receiving treatment and shorter time to treatment than the experimental arm because of anxiety.

QOL: Quality of life (anxiety and depression, prostate cancer symptom checklist) will be compared between the two arms. The time trajectory of QOL will be estimated using the generalized estimating equation method based on working independent correlation structure (103) and the slope of the time trajectory will be compared between the two arms (104). We will consider taking a log-transformation of QOL observations if it improves the linearity of the time trajectory of QOL. The significance of the two arm comparisons will be adjusted for multiple testing among different QOL subscales using the methodology of Bang, Jung and George (105).

Dietary Recall: Diets will be evaluated at baseline and at 12 and 24 months by a series of three separate 24-hour dietary recalls collected interactively via telephone interview. The increase (from baseline) in mean daily intakes of total vegetables, crucifers, tomato products, beans/legumes and fat will be compared between arms using a two-sample t-test at 12 and 24 months. We may consider transforming (e.g. using logarithm) the data to improve normality of the distributions and variance stabilization. Data will be catalogued and analyzed utilizing Minnesota Nutrition Data System (NDS) software (Nutrition Coordinating Center, University of Minnesota).

Plasma carotenoid analyses:

- (1) Plasma carotenoid concentrations (PCC) will be compared between the two arms using a two-sample t-test. A log-transformation of the PCC observations may be considered in order to improve the normality of the distributions and variance stabilization.
- (2) PCC will be correlated with PSADT for the patients. Descriptive analysis using scatter plots and regression analysis will be conducted. Intervention and known predictors including the stratification factors will be adjusted in multivariable analysis.

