11.5 Statistical analyses for substudy 151105

For Objective 10.3.2.1, the expression level of MnSOD, XRCC1 and GST will be correlated with PSADT within each arm. The expression level of these genes may be highly correlated with PSADT in the control arm. However, if dietary modification alters the genetic risk, the association may be insignificant or less significant in the experimental arm.

For Objective 10.3.2.2, the expression level of MnSOD, XRCC1 and GST will be correlated with time to pathological progression using Cox regression method within each arm. The expression level of these genes may be highly correlated with time to pathological progression in the control arm. However, if dietary modification alters the genetic risk, the association may be insignificant or less significant in the experimental arm.

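### The gene analyses in Section 11.5 name no covariate, so a within-arm gene association can partly reflect race: a small, cheaply closed gap in the correlative substudy

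*Combined protocol and SAP*

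**What the plan says.** Section 10.3.2 sets two objectives for the polymorphism work. The first is "To compare MnSOD, XRCC1, and GST gene polymorphisms to PSADT in AS patients receiving dietary intervention versus no intervention". The second is "To compare MnSOD, XRCC1, and GST gene polymorphisms to time to pathological progression in AS patients", again by arm.

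Section 11.5 is the only analysis plan for them. For the first objective, "the expression level of MnSOD, XRCC1 and GST will be correlated with PSADT within each arm". For the second, the same quantities "will be correlated with time to pathological progression using Cox regression method within each arm". It names no covariate for either, and neither Section 10.3.2 nor Section 10.3.3 supplies one.

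Section 11.3 treats the same two outcomes differently when the predictor is plasma carotenoid concentration: "Intervention and known predictors including the stratification factors will be adjusted in multivariable analysis". The multivariable Cox model for the main progression endpoint also adjusts for the stratification factors. Sections 5.7 and 11.1 list race (Black or African American against other) among those factors. The adjustment statements in Section 11.3 belong to those analyses, and nothing carries them over to Section 11.5.

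On race and disease, Section 1.9 refers to "The increased risk of prostate cancer and especially of lethal prostate cancer among African Americans". Its enrolment table plans 54 Black men among 464, and its text gives a goal of 29% for all racial minorities together.

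**The concern.** Stratified randomisation makes the two arms alike in race. It does not break a link between genotype and race inside an arm, because genotype is not assigned by randomisation. Each within-arm analysis therefore contains the full race mixture. If an allele is more common in Black men, and Black men progress at a different rate, the allele will be associated with progression even when it does nothing.

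Section 11.5 reads its results from how strong or significant the association is in each arm, and Section 10.3.1 hopes to identify genetically high-risk men. An association that partly marks race would mislead on both counts. The factor that would remove most of this is already recorded for every man and is already used for the carotenoid models.

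**Working it through.** The plan gives no sample size, power or effect size for the gene analyses, so there is no figure to reproduce. The calculation below is an illustration under stated assumptions, with no true gene effect.

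**Inputs from the documents**
- Share of Black men, p = 54/464 = 11.6% (Section 1.9). Upper bound 29%, reached only if the whole minority goal were met by Black men.
- Men per arm: 418 × 0.8 = 334, and 334/2 = 167. The 80% participation is stated in Section 10.4.4 for the biopsy work; I assume it holds for the gene work.
- Pathological events: Section 11.3 uses a 10% two-year control rate as an example, and 167 × 0.10 ≈ 17.

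**Assumptions not in the documents**
- PSADT: allele frequency f0 = 0.2 in other men and f1 = 0.3 to 0.6 in Black men; race difference d = 0.25 to 0.5 SD in log-PSA slope.
- Pathological progression: carrier frequencies of 50% vs 40%, 60% vs 30% and 70% vs 20% (Black vs other); race hazard ratio 1.5 to 2.

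**PSADT test (gene coded 0, 1, 2, unadjusted)**
- cov = p(1−p) × 2(f1−f0)
- var(G) = p·2f1(1−f1) + (1−p)·2f0(1−f0) + p(1−p)·4(f1−f0)²
- spurious slope b = d × cov/var(G)
- residual variance v = 1 + p(1−p)d² − b²·var(G)
- shift of the test statistic = b × √(167 × var(G)/v)

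Low corner (p = 0.116, f1 = 0.3, d = 0.25): cov = 0.0206, var(G) = 0.3358, b = 0.0153, v = 1.006. The shift is 0.0153 × √(167 × 0.3358/1.006) = 0.11, giving a type I error of about 5.1%.

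High corner (p = 0.116, f1 = 0.6, d = 0.5): cov = 0.0823, var(G) = 0.4044, b = 0.1017, v = 1.0215. The shift is 0.1017 × √(167 × 0.4044/1.0215) = 0.83, giving about 13.1%.

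| f1 (f0 = 0.2) | 11.6% Black, d = 0.25 / 0.5 | 29% Black, d = 0.25 / 0.5 |
|---|---|---|
| 0.3 | 5% / 6% | 6% / 7% |
| 0.4 | 6% / 7% | 7% / 13% |
| 0.5 | 6% / 10% | 9% / 22% |
| 0.6 | 7% / 13% | 12% / 32% |

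Simulating 4,000 arms of 167 men per scenario agrees within simulation error: about 5 to 14% at the planned share and about 31% in the extreme corner. With race in the model, rejection is about 4 to 6% throughout.

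**Pathological progression (carrier vs non-carrier, unadjusted)**

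Crude HR = [(p·pB·R + (1−p)·pO)/pc] ÷ [(p(1−pB)R + (1−p)(1−pO))/(1−pc)], where pB and pO are the carrier frequencies in Black and other men, R is the race hazard ratio and pc is the overall carrier frequency. The shift is √(17·pc(1−pc)) × |log HR|.

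Example (p = 0.116, 60% vs 30%, R = 2): pc = 0.335; HR = 1.208/1.070 = 1.13; shift = √(17 × 0.335 × 0.665) × log 1.13 ≈ 0.24; type I error 5.6%.

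Over the grid the spurious HR is 1.02 to 1.26 and the type I error 5.0 to 7.0% at 11.6% Black men. At 29% they are 1.04 to 1.40 and 5.1 to 10.2%. If carrier frequency is equal across races, or R = 1, the bias is nil.

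**The case against.** **Neither half of the mechanism is documented for these outcomes.** This stands. Section 1.9 concerns the risk of getting prostate cancer and of lethal disease. A reader might infer that the protocol itself states a race difference in progression on surveillance. It does not, and these men are selected for low-risk disease. No allele frequency by race is given for any of the three genes. The point is therefore conditional.

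**The size is modest at planned enrolment.** This also stands. A rejection rate near 32% needs three extremes at once: 29% Black men, allele frequency 0.6 against 0.2, and a 0.5 SD race effect. The enrolment table plans 11.6%.

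**The between-arm question is largely protected.** A reader might infer that a false gene signal would become the substudy's conclusion. The documents do not support that. The stated interest is whether diet alters genetic risk, and the same race-induced bias is expected in both arms, so it should cancel in a direct contrast. In simulation, a between-arm test of the gene slopes rejected 4.7 to 5.5% of the time in every scenario tried. However, Section 11.5 plans no such contrast and compares significance arm by arm, so the within-arm inflation remains under the plan as written. Race adjustment does not repair that separate weakness.

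**Adjustment is not free in the Cox model.** This stands in part. About 17 events spread over the gene and three stratification factors is about 4 events per parameter. With about 19 Black men per arm (0.116 × 167), a 10% rate gives about 2 events among them. That argues against all three factors. It does not argue against stratifying on race alone.

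**The good adjusted error is built in**, because race is the only confounder simulated. True: men classed as other are themselves of mixed ancestry, and some confounding could remain.

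**Conclusion.** The omission is plain on the text and inconsistent with how Section 11.3 handles the same outcomes. Within an arm, a gene association can partly reflect race if both allele frequency and progression differ by race. Under the assumptions above, and at the planned 11.6% Black share, the nominal 5% PSADT test runs at about 5 to 14%, and the pathological progression test at about 5 to 7%. Larger figures need a share near the 29% upper bound as well as wide allele and risk differences. This is a minor point about a correlative substudy. It does not touch the primary analysis or any sample-size figure.

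**What to change.** In Section 11.5, state that every gene model includes the race stratum (Black or African American against other): as a covariate in a regression of log-PSA slope for PSADT, and as a stratum in the Cox model for pathological progression. Add one sensitivity analysis restricted to the larger race group. Do not require the other stratification factors in the Cox model, given the few pathological events.

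In the same edit, reconcile the analysed variable: Section 11.5 speaks of expression level, while Sections 10.3.2 and 10.3.3 describe polymorphisms measured on DNA.

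The cost is wording only, since race is collected at randomisation. Some precision is lost where genotype and race are correlated, and ancestry differences within the other group remain. Prespecifying the adjustment also removes a later choice between adjusted and unadjusted results.
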